## INTRODUCTION

Chronic venous insufficiency (CVI) of the lower limbs is a common condition affecting 5–30% of the adult population worldwide, with a prevalence that is consistently increasing with age (1-5).

The ultimate stage of CVI (the C6 stage) according to the CEAP classification (clinical, etiological, anatomical and pathophysiological) is represented by the venous leg ulcer (VLU), which can often take several months or even years to heal; only 30–75% of patients seem to achieve wound closure after six months of treatment, depending on the severity of the ulcer and the patients' health status (6,7).

According to guidelines, and based on systematic reviews, the management of these wounds requires a holistic approach, combining suitable local wound care with an adapted aetiological treatment based on an effective and high compression therapy applying 40 mmHg at the ankle in the acute decongestion phase of oedema and for the treatment of an active VLU (8).

Very positive clinical outcomes provided by a randomized controlled trial involving 187 patients comparing a four-layer bandage with a two-layer bandage compression system UrgoK2 (9) as well as a very large clinical evaluation including 702 patients treated under real-life conditions, have confirmed the efficacy and safety profile of this multicomponent compression system (10). Both of these clinical evaluations have supported the efficacy of this high compression therapy in healing VLUs, reducing lower limb oedema caused by CVI and improving the Quality of Life of patients. The real-life study even brought growing evidence supporting the use of this compression system, as a first-line intervention (higher healing rate when used in first intention) in the treatment of VLUs.

Venous leg ulcers are characterized by elevated and prolonged expressions of matrix metalloproteinases (MMPs) in the wound tissue and fluid which have been correlated to the impaired healing and chronicity and mixed arterial ulcers also have an impaired perfusion (11). Addressing this protease imbalance by reducing the high levels of MMPs could represent a possible therapeutic modality to improve ulcer healing (12-13).

Wound dressings including the Technology Lipido-Colloid with Nano Oligo Saccharide Factor (TLC-NOSF) are known for their protease inhibiting properties and positive impact on chronic wound healing; their efficacy and acceptability for patients and caregivers, when associated with good

standards of care, have been documented in a pooled data analysis from eight European non-interventional studies (real-life studies), including nearly 8,000 patients presenting with venous leg ulcers (14).

Additionally, clinical evidence in VLUs has been recently highlighted in the United Kingdom, by the National Institute of Health and Care Excellence (NICE), in its related evidence-base guidance (15). NICE stated that the interactive UrgoStart dressings (Technology Lipido-Colloid with Nano Oligo Saccharide Factor) improves wound healing in venous leg ulcers when used as part of overall management including compression therapy, and thus is likely to be cost-saving in addition to an improved quality-of-life. These recommendations were based on the clinical data provided through two randomized controlled trials which evaluated the impact on venous leg ulcers treated with UrgoStart dressings (16,17).

On this basis, we strongly believe that the combination of Urgo K2 and UrgoStart wound dressings could represent an optimal alternative to manage venous leg ulcers for which high compression application is needed. So, the objective of this clinical investigation is to assess the therapeutic safety and efficacy of this new “global solution” (high compression and interactive wound dressing) in such chronic wounds, when used as a first intention treatment.

## **1. STUDY DESIGN**

This clinical investigation is an open non-comparative monocenter clinical trial conducted in England. The investigation will be conducted in the Gloucestershire Leg Ulcer Service, at Cheltenham General Hospital and Gloucestershire Royal Hospital (UK).

This clinical trial will include 60 patients; they will be outpatients, community treated, and will be followed for a maximum duration of twelve weeks.

The inclusion period will last a maximum of 12 months.

## 2. STUDY OUTCOMES

### 2.1. PRIMARY OUTCOME

The primary endpoint of this clinical investigation is to assess the efficacy of a global treatment for venous leg ulcers, comprising a combination of a multilayer high compression system, UrgoK2® in addition to an interactive dressing, named UrgoStart® Plus (Pad and Border).

The Main efficacy criteria will be complete ulcer closure (100% re-epithelialisation) after a maximum of 12 weeks treatment period.

### 2.2. SECONDARY OUTCOMES

The secondary criteria are to determine the following:

- Time to reach complete wound closure,
- Relative (and absolute) wound surface area reduction ( $\text{area}_{t0} - \text{area}_{t\text{last}}$ ),
- Percentage of patients with a  $\geq 30\%$  wound area reduction  $[(\text{area}_{t0} - \text{area}_{t\text{last}}) / \text{area}_{t0} \times 100]$  at Week 4 (18,19).
- Evolution of the ankle circumference,
- Patient Quality of Life through a specific the WoundQuol Questionnaire,
- The safety of the tested procedure (compression therapy system and dressings) through the nature and number of emergent local adverse events (i.e., events not present at baseline),
- Patients' acceptability of the procedure, evaluated by the investigator and by the patient,
- The change frequency per week over the treatment period.

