### **1.2.3. Characteristics of the lesion**

The following will be documented:

- The nature and location of the lesion,
- The clinical status of the wound (presence of sloughy tissue, granulation tissue and necrotic tissue, on the wound bed),
- The condition of the surrounding skin,
- The history of the lesion (duration, recurrence, previous treatment...).

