### 6.2. SECONDARY CRITERIA

The secondary criteria are to assess or to measure the:

- Time to reach complete wound closure,
- Relative and Absolute wound surface area reduction ( $\text{area}_{t0} - \text{area}_{t\text{last}}$ ),
- Percentage of patients with a  $\geq 30\%$  wound area reduction  $[(\text{area}_{t0} - \text{area}_{t\text{last}}) / \text{area}_{t0} * 100]$  at Week 4,
- Evolution of the ankle circumference,
- The Patient Quality of Life through a specific the WoundQuol Questionnaire,
- The safety of the procedure (nature and number of emergent local adverse events),
- Patients' acceptability to the studied procedure (compression system and dressing) evaluated by the investigator and by the patient,
- The dressing change frequency.

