## 7. LOCAL ADVERSE EVENTS

Any local adverse event (LAE) occurring during the tested treatment, irrespective of its severity, must be recorded in the case report form, in the pages provided for this purpose.

The onset of an adverse event may lead to a withdrawal of the study treatment, either temporarily or definitively.

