### **The following will be recorded:**

- The nature and date of onset,
- The causal relationship with current treatment,
- The outcome,
- The therapeutic decision.

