## 8. INTERCURRENT ADVERSE EVENTS

Any untoward intercurrent medical occurrence in a patient or clinical investigation subject administered an investigational product and which does not necessarily have a causal relationship

with this treatment will be considered as an Intercurrent Adverse Event. An intercurrent adverse event (IAE) can therefore be any unfavourable and unintended sign (including an abnormal laboratory finding, for example), symptom, or disease temporarily associated with the use of an investigational product, whether or not considered related to the tested procedure.

Any intercurrent adverse event occurring during the treatment will be recorded in the Case Report Form, in the pages provided for this purpose.

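### The only safety outcome counts new local events, so on a literal reading it omits worsening of local problems present at Day 0 and all non-local events

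*Protocol*

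**What the plan says.** Section 2.2 lists one safety criterion among the secondary outcomes: the "nature and number of emergent local adverse events (i.e., events not present at baseline"). Section 6.2 restates it as "The safety of the procedure (nature and number of emergent local adverse events"), without the explanation of emergent. No other safety outcome is named.

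The stated aim is wider. According to the Introduction, "the objective of this clinical investigation is to assess the therapeutic safety and efficacy of this new" combined treatment, that is, high compression together with the interactive dressing.

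Collection is also wider than the outcome:

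- Section 7: "Any local adverse event (LAE) occurring during the tested treatment, irrespective of its severity, must be recorded in the case report form". The items to be recorded are the nature and onset date, "The causal relationship with current treatment", the outcome and the therapeutic decision. Severity is not in that list.
- Section 8: "Any intercurrent adverse event occurring during the treatment will be recorded in the Case Report Form". The definition there applies whether or not the event is thought to be related to the procedure.
- Section 9: serious events go to the principal investigator by telephone within 48 hours.
- Section 1.2.3 (under 5.2): "The condition of the surrounding skin" is documented at Day 0, so a local baseline exists.

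Section 10.2.1 describes the analysis as covering the primary and secondary objectives. Section 10.3.1 defines a Safety population of all included and treated patients.

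**The concern.** Section 2.2 explains emergent with an *i.e.*, which makes the phrase a definition and not an example. Under that definition, a local problem that is mild at entry and becomes worse under the devices was present at baseline and drops out of the count. Every patient enters with an open ulcer. Clinically infected ulcers and ulcers covered by black necrosis are excluded (section 4.3), but existing dermatitis, maceration or pain is not. Section 3.3.2 allows topical treatments around the lesion, corticosteroids among them, so the plan itself expects some patients to have peri-ulcer skin that needs care. In these patients the rule would understate local harm.

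The second restriction, to local events, means that an intercurrent event contributes nothing to the safety outcome even if the investigator judges it related to the procedure. In a single-arm study whose stated objective includes safety, the reported safety result would then describe new local events only, while a reader would take it as the safety of the combined treatment.

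**Working it through.** The protocol gives no event rates and no figure to reproduce for this criterion, so the check compares what is collected with what the outcome counts.

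| Type of event | Collected? | In the safety outcome as worded? | Where else it would appear |
|---|---|---|---|
| New local event, not serious | Yes (section 7) | Yes | Discontinuation listing if it causes withdrawal |
| New local event, serious | Yes (sections 7 and 9) | Yes; seriousness is no exclusion | Same |
| Worsening of a local condition present at Day 0, serious or not | Yes, if the investigator regards it as an event (section 7); otherwise through visit descriptions and photographs | No, read literally | Same |
| Non-local event, not serious | Yes (section 8) | No | Same |
| Non-local event, serious | Yes (sections 8 and 9) | No | Same |

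The last column rests on section 5.4, where local events requiring permanent discontinuation and intercurrent events requiring withdrawal are listed reasons, and on section 10.3.2, where discontinued patients are listed with their reason.

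**Step 1: is worsening brought back in elsewhere?** Section 6.2 repeats emergent without redefining it. Section 7 governs what is recorded, not what the outcome counts. No section states that worsening is emergent.

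**Step 2: can worsening be reconstructed from what is recorded?** Partly. The event items in section 7 carry no severity, although the section refers to it ("irrespective of its severity, must be recorded in the case report form"). Other records help: lesion characteristics at each visit (5.3), photographs at baseline and each visit (1.2.5, 5.3), a clinical and photographic assessment of each local event (7), and pain and maceration under acceptability (5.3, assessed qualitatively). None of these is a severity grade attached to the event.

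**Step 3: are non-local events brought back in elsewhere?** They are recorded or reported, and some reach the discontinuation listing. They belong to no primary or secondary outcome, and section 10.2.1 names only those objectives.

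**Step 4: size.** The protocol states neither the share of patients with a local problem at Day 0 nor the share likely to worsen, so the expected number of uncounted patients cannot be derived. For scale only: if all 60 planned patients are in the Safety population, each patient whose only event is of an uncounted type lowers the reported proportion with an event by 1/60 = 1.7 percentage points.

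**The case against.** The strongest reply has four parts.

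1. *The data are not lost.* Local, intercurrent and serious events are all recorded or reported, and the most consequential ones, those that end treatment, are listed by patient with the reason. This stands. It confines the point to the outcome definition.

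2. *Worsening is followed by other routes.* Lesion descriptions, photographs and the acceptability items track skin, pain and maceration, and the Wound-QoL asks about pain and discharge at Day 0 and at the end. This stands in part. The information feeds other outcomes or remains descriptive; the safety count does not use it, and no graded comparison with Day 0 is built in.

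3. *The literal reading is not the only one.* The text speaks of events, and a flare that begins on treatment could be called an event that was not present at baseline. That is fair. But if two analysts can count the same flare differently, the definition needs the same repair.

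4. *A local criterion suits a bandage and a dressing, and tabulation of the rest belongs in a statistical analysis plan.* How the other events are tabulated may indeed be set out there, and its absence here is no finding. The point is different: the protocol itself fixes the safety outcome, and fixes it more narrowly than its own objective.

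A reader might infer that all serious events escape the safety outcome. The documents do not support this: a serious event that is local and new is counted. A reader might also infer that worsening cannot be recovered at all, or put a number on the patients missed. Neither follows. The first overlooks the visit records, and the second would rest wholly on assumed rates.

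**Conclusion.** The point holds as a defect in the wording of one secondary outcome. Read literally, the safety criterion omits worsening of a local condition present at Day 0 and every non-local event, serious or not, while the objective is the safety of the whole procedure and the events are already being captured. New local events are counted whether serious or not, and events leading to withdrawal remain visible in the discontinuation listing.

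The direction is clear: the reported event count can only be too low relative to the objective. The size is not known, since the protocol offers no rates. The worsening part rests on taking the explanation in section 2.2 as a definition; under the looser reading it becomes an ambiguity with the same remedy. The non-local part needs no such assumption. This is a cheap improvement worth making; it does not show that the trial fails to monitor harm.

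**What to change.** - In sections 2.2 and 6.2, define emergent in the same words: *not present at baseline, or present at baseline and worsened on treatment*.
- In section 7, add severity to the items recorded for each local event, so that worsening can be judged against the Day 0 description of the lesion and surrounding skin.
- In sections 2.2 and 6.2, extend the safety outcome to all adverse events recorded under sections 7 to 9, with local events shown as a subset, summarised on the Safety population already defined in section 10.3.1.

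The cost is one CRF field, some additional tabulation and a slightly less favourable event count. Most of the data are already collected, and neither the sample size nor the visit schedule changes.

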## 3. COMPOSITION AND CHARACTERISTICS OF THE STUDY TREATMENT

The study treatment is based upon a combination of a compression therapy system composed of a two layers compression therapy system (Urgo K2®) and an interactive wound dressing from the UrgoStart® range (UrgoStart® Plus Pad and UrgoStart® Plus Pad Border). Regarding the compression, UrgoK2® is a two-layer compression bandage system, which benefits from the exclusive technology of the pressure system. The pressure system has been specifically designed to aid the application of the recommended therapeutic pressure (average 40 mmHg) for venous leg ulcers presenting an ABPI (Ankle Brachial Pressure Index) superior to 0.8 value, from the first application.

### **3.1. THE TWO LAYER COMPRESSION SYSTEM**

The Urgo K2® compression therapy system is indicated in the treatment of venous leg ulcers which require a high level of compression and presenting with Ankle Brachial Pressure Index (ABPI) > 0.85. This compression system is described in Appendix 1 of this current clinical trial Protocol.

### **3.2. URGOSTART RANGE DRESSINGS**

The UrgoStart® dressings represent a local treatment to enhance the healing process and to reduce healing time of chronic wounds such as leg ulcers, diabetic foot ulcers and pressure sores, due to the TLC-NOSF Healing Matrix, to be part of a good standard of care (including compression in the case of venous leg ulcers).

This dressings range (two different dressings) is described in Appendix 2 of this current clinical trial Protocol.

At any time of the 12 weeks treatment, a switch from one UrgoStart dressing to another one (Pad to Pad Border for example) can be done, at the convenience of the investigating caregiver.

### **3.3. CONCOMITANT TREATMENTS**

#### **3.3.1. General**

The studied procedure (UrgoK2®/UrgoStart®) does not present any contra-indications to the use of a systemic treatment, irrespective of the therapeutic class.

The existence of general treatments at the time of inclusion in the investigation, along with any modifications during it, must be documented in the case report form (CRF).

#### **3.3.2. Local treatments**

Wounds will be cleansed with saline solution where appropriate.

The use of local antiseptics, if deemed necessary by the investigator, must be documented in the case report form.

Other local treatment (water, pastes, zinc pastes, corticosteroids, etc.) are permitted for application around the lesions: their use must be documented in the case report form.

## 4. PATIENT SELECTION

### 4.1. INITIAL SELECTION DIAGNOSIS

The patients recruited for this clinical investigation will be patients treated on an outpatient basis for a venous leg ulcer presenting with an ABPI>0.85 (venous origin).

### 4.2. INCLUSION CRITERIA

#### **Related to the patient:**

- Patient over 18 years old who has provided his/her written informed consent,
- Patient who is able and willing to commit to regular follow up with the investigating team for the purpose of the study, and in line with established service protocols for routine patient follow up until ulcer healed,
- Patient who agrees to adhere to the study protocol with respect to the type of multilayer compression system and primary wound dressing,

#### **Related to the venous leg ulcer:**

- Ulcer between 2 and 20 cm^2 in surface,
- Ulcer duration less than six weeks ("new ulcer"),
- Venous leg ulcer - Ankle Brachial Pressure Index > 0.85 at baseline, done in the previous three months and if not, at the inclusion of the patient),

### 4.3. EXCLUSION CRITERIA

#### **Related to the patient:**

- Patient participating in another clinical trial,
- Patient with known hypersensitivity to one of the components of the tested compression system Urgo KTwo Lite Latex free or the UrgoStart dressings,
- Patient who is unable to tolerate compression therapy,
- Patient presenting a neoplastic lesion treated by radiotherapy or chemotherapy or patients treated with immunosuppressive drugs or high-dose corticosteroids,
- Patient with a history of deep or superficial vein thrombosis in the 3 months prior to inclusion,
- Patient confined to bed.

**Related to the leg ulcer:**

- Ulcer with ABPI<0.85,
- Ulcer which is clinically infected,
- Ulcer surface area partially or totally covered by black necrosis plaque,
- Malignant ulcer,
- Ulcer less than 3 cm, from any edge, to another wound located on the same limb.

**NB:** In the case of a patient presenting with several ulcers located on the same limb, the investigator must select at the inclusion visit only one wound for the evaluation (target ulcer), which best meets the selection criteria. This ulcer will be distant from the edge of any other wound on the same limb by a minimum of 3 cm. The other wound(s) will be treated with the investigator's usual treatment procedures for the primary wound dressing (*i.e.*, the compression system being the same for one entire lower limb).

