## 6. ASSESSMENT CRITERIA

### 6.1. MAIN CRITERION

The main judgment criterion is the completely closed study ulcer (100% re-epithelialization) evaluated at last available study visit (12 weeks, at the latest).

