## **10. STATISTICAL ANALYSIS**

### **10.1. NUMBER OF SUBJECTS**

Given the uncontrolled nature of this clinical study, the data available in the literature in this area, and the treatment duration of twelve weeks for each patient, it appears that the total number of 60 patients is sufficient to provide a relevant answer to the primary endpoint. This has been agreed with our medical statistician who is independent of this study.

No statistical tests will be applied because this clinical study is non-comparative.

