### **10.2. DATA MANAGEMENT AND STATISTICAL ANALYSIS**

#### **10.2.1. Statistical analysis plan (SAP)**

The statistical analysis of this study will be performed by the principal investigator at the end of the trial, for all the primary and secondary objectives.

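### When several ulcers on a limb qualify, the target-ulcer rule sets no order among them, so the open-label investigator's choice can move the single-arm closure rate either way

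*Protocol*

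**What the plan says.** Protocol section 4.3 (note under the leg-ulcer exclusions) deals with the patient whose limb carries several ulcers: "the investigator must select at the inclusion visit only one wound for the evaluation (target ulcer), which best meets the selection criteria". The note adds the 3 cm separation from other wounds. The remaining wounds get the investigator's usual primary dressing under the same compression.

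The ulcer criteria are in sections 4.2 and 4.3: area from 2 to 20 cm², "Ulcer duration less than six weeks", ABPI above 0.85, no clinical infection, no black necrosis, not malignant, and at least 3 cm from another wound. Section 5.1 admits a patient only once every criterion is satisfied.

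Section 1 describes the design: "This clinical investigation is an open non-comparative monocenter clinical trial conducted in England", and "This clinical trial will include 60 patients". Section 6.1 defines the endpoint on the selected ulcer alone: "The main judgment criterion is the completely closed study ulcer (100% re-epithelialization) evaluated at last available study visit (12 weeks, at the latest". Section 10.1 adds "No statistical tests will be applied because this clinical study is non-comparative".

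At Day 0 the number of ulcers on the studied limb is recorded (section 1.2.2, within 5.2). Duration and ruler area are specified for the lesion under study (sections 1.2.3 and 1.2.4).

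**The concern.** The rule uses a superlative, but the criteria it points to have no degrees. An ulcer of 3 cm² and one of 18 cm², both five weeks old, clean and well separated, pass equally. The rule gives no reason to take one over the other, so the decision falls to an investigator who knows the treatment and can see both wounds.

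In a randomised trial such a choice, made before allocation, would affect both arms alike. Here there is one arm and no planned test, so the observed closure percentage is itself the result and is read as an absolute figure. Any consistent preference for easier or harder ulcers enters it directly.

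An analysis plan cannot repair this afterwards. Once the target is chosen, the other eligible ulcers are neither assigned the study dressing nor required to be measured, so the result under a neutral choice cannot be recovered.

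**Working it through.** **Step 1. Can the criteria rank two eligible ulcers on one limb?**

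- Area and duration are given as limits. Nothing says that smaller, larger, newer or older is better.
- ABPI is a property of the limb, so it is the same for both ulcers.
- The 3 cm distance in the note repeats an exclusion criterion, so every eligible ulcer already satisfies it.
- Infection, black necrosis and malignancy are yes/no exclusions.

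No criterion separates the two ulcers, and the protocol gives no ranking or random choice elsewhere. If only one ulcer qualifies, the rule is fully determinate.

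**Step 2. Could the choice matter?** The Introduction says closure depends on ulcer severity and gives 30–75% at six months. The eligible area range is 20/2 = tenfold. That the larger of two eligible ulcers closes less often is an assumption here, not a figure in the protocol.

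**Step 3. How large could the shift be?** The protocol states no closure rate to reproduce, and it does not give the inputs needed for the shift. The following are assumptions:

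- m = share of patients with two eligible ulcers on the limb, 5–40%
- d = difference in 12-week closure between the easier and the harder ulcer, 10–20 points

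Patients with one eligible ulcer contribute the same under any rule and cancel out. In the others, a neutral (random) pick closes at the average of the two probabilities. Therefore:

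- always easier versus neutral pick: m × d / 2
- always easier versus always harder (taken to be the larger): m × d

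| m | d (points) | versus neutral | extra closures in 60 | versus always larger |
|---|---|---|---|---|
| 5% | 10 | 0.25 | 0.15 | 0.5 |
| 5% | 20 | 0.5 | 0.3 | 1.0 |
| 20% | 10 | 1.0 | 0.6 | 2.0 |
| 20% | 20 | 2.0 | 1.2 | 4.0 |
| 40% | 10 | 2.0 | 1.2 | 4.0 |
| 40% | 20 | 4.0 | 2.4 | 8.0 |

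A preference for harder ulcers gives the same shift against a neutral pick with the opposite sign.

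As an outer bound only, take the Introduction's extremes as the two probabilities (d = 75 − 30 = 45). The shift against a neutral pick is then 0.10 × 45 / 2 = 2.25 points at m = 10% and 0.40 × 45 / 2 = 9.0 points at m = 40%. Those extremes are six-month figures across patients, not 12-week figures for two ulcers on one leg.

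**Step 4. Scale.** With 30 closures in 60, the 95% interval is 37.7–62.3% (Wilson) or 36.8–63.2% (exact), a half-width of 12.3 or 13.2 points. The largest main-range shift against a neutral pick is 4/12.3, about one third of the Wilson half-width. Against always taking the larger it is 8/12.3, about two thirds. Unlike sampling error, this shift does not shrink with more patients.

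**The case against.** **The rule fixes a good deal.** It requires one ulcer, chosen at inclusion before treatment and at least 3 cm from other wounds, and it leaves no choice when only one qualifies. This stands. The gap is confined to patients with two or more eligible ulcers on the limb.

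**Such patients may be few.** Each ulcer must pass every criterion, including a duration under six weeks. This also stands, and is why the range for m starts at 5%, where the shift against a neutral pick is at most half a point.

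**No decision rests on the result.** There is no test or success threshold, and the size and duration of the target ulcers can be tabulated at baseline. This is partly right. The tabulation shows which ulcers were studied, but not which eligible ulcers were passed over.

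**Stronger readings the documents do not support.**

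- A reader might infer that the closure rate will be inflated. The protocol permits a preference but does not steer it, and a preference for harder ulcers would lower the rate.
- A reader might infer that one person treats, judges closure and analyses. Section 10.2.1 says the analysis "will be performed by the principal investigator at the end of the trial", and the investigator selects and assesses the ulcer. Section 4.2 refers to an investigating team, however, and care between visits is given by a community nurse (section 5.2, Appendix vi). Nowhere is it said that one person does all three.
- A reader might take 0.5–8 points as the inflation. That range compares the easier ulcer with the harder one. Against a neutral choice it is half as large.

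**Conclusion.** The point holds in a limited form. Where two or more ulcers on a limb are eligible, the selection sentence gives no order and the open-label investigator has free choice. Because the choice is made at baseline, it is possible prognostic selection. It matters because the single-arm closure rate of the chosen ulcers is the primary result.

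The size is unknown. With 5–40% of patients affected and a 10–20 point difference in closure, both assumed, the effect of always choosing the easier ulcer runs from negligible to 4 points against a neutral pick. That is smaller than the sampling uncertainty at 60 patients, but it is systematic and cannot be corrected after Day 0. This is a cheap improvement, not a defect that invalidates the trial.

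**What to change.** In the note to section 4.3, replace the best-match clause with a rule that two people would apply identically at Day 0. Either of these would do:

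- the largest ulcer by ruler area that meets all criteria, with ties going to the oldest; or
- a random choice among the ulcers that meet all criteria, by a method fixed in advance.

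The random choice is neutral. The largest-ulcer rule is simpler to audit and conservative: under the assumptions above it gives a closure rate about 0.25–4 points below a neutral pick.

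At Day 0, record the ruler area and duration of every eligible ulcer on the limb, since at present only the number of ulcers is required. Report closure separately for patients with one and with several eligible ulcers.

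The cost is one changed sentence, a few extra CRF fields, a short additional measurement in the patients concerned and, under the largest-ulcer rule, a somewhat lower reported rate.
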